The use of saliva stimulating drug shave the potential of confounding the degree of xerostomia experience by the subject due to radiotherapy. Because of this, these type of drugs are not allowed during the duration of the subject's participation in the clinical trial. Symptomatic relief of xerostomia will be approached using medications that do not stimulate the production of saliva. Such drugs include artificial salivas and Biotene oral spray. Potential subjects who are currently using saliva stimulating drugs must discontinue the drugs to qualify for the study. A washout period of 3-5 days is required.

4. Unable to receive standard chemotherapy

INVESTIGATIONAL PLAN

Upon consenting to the study, the subject will complete a series of questionnaires, including the subjective LENT/SOMA xerostomia form, the University of Michigan's XQ, and the EORTC QLQ-C30 and H&N35 modules. Then the subject will attend their scheduled routine chemotherapy as prescribed by the treating medical oncologist. This will be given concurrently with radiation therapy as discussed with the Radiation Oncologist.

Following the completion of the scheduled chemo-radiotherapy, the subject will be seen in Radiation Oncology every 3 months for routine follow-up visits related to their radiation treatment. During those visits, the subjects will once again complete the packet of questionnaires. The EORTC questionnaires and the xerostomia assessments (the LENT/SOMA form and the XQ) will also be filled out at 3 months (+/- 30 days), 6 months (+/- 30 days), 9 months (+/- 30 days) and 12 months (+/- 30 days) after chemo-radiotherapy. The packet will be completed in the clinic, but if necessary can be sent home with the subject with a return envelope, emailed to the subject, or the subject may be called to respond to the questions over the phone. The subject is also to be seen at the discretion of the medical oncologist and surgeon as part of routine oncologic follow-up.

Duration of follow-up

The subject will not be followed after the completion of the questionnaires at the 12 month visit.

Removal of subject from study

Subjects will be removed from the study when any of the criteria listed below apply:

- Subject withdraws consent from study;
- Subject is unable to comply with protocol requirements;
- Subject experiences toxicity that makes continuation in the protocol unsafe;
- Treating physician judges continuation on the study would not be in the subject's best interest;

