- Subject becomes pregnant (pregnancy to be reported along same timelines as a serious adverse event).

The Principal Investigator will be notified, and treating physician will document the reason for study removal and the date the subject was removed in the subject's medical record. The study coordinator will record the reason for removal and date in the Case Report Form (CRF).

STUDY PROCEDURES

Investigator will use one of the two strategies (i.e. Margin based or Robust) to plan for radio-therapy. Both of the strategies are standardly used at UAMS. Generally, it is just a physician's preference that determines which is used.

Margin-based and robust radiotherapy are both standard ways of delivering radiotherapy; therefore, no protocol-specific procedures are required with the chemo-radiotherapy.

The EORTC questionnaires and the xerostomia assessments will be filled out at 3, 6, 9 and 12 months after chemo-radiotherapy.

Radiotherapy

Subject will receive either routine margin-based or robust radiotherapy. The selection of which type of planning will be assigned to a subject will be determined in a 1:1 randomized fashion with stratification by primary tumor site.

Follow-up visits

Subjects will be seen in Radiation Oncology every 3 months for one year. Adverse events will be assessed during routine physical exams at each visit. In addition, at the time of each visit the subject will complete the EORTC quality of life-30 questionnaire and associated module HN-35 module, and subjective LENT/SOMA xerostomia scoring form.

MEASURES

Xerostomia: The Late Effects of Normal Tissues Subjective-Objective Management Analytic (LENT-SOMA) system includes subjective (patient-rated) and objective (clinician-rated) indices of radiotherapy toxicities [23]. The patient-rated xerostomia item is used in the current study. The item is rated on a 4-point Likert scale with 1 being the minimum and 4 being the maximum grades shown on the form. Evidence supports the convergent and construct validity of this measure [22, 23]. The University of Michigan's Xerostomia Questionnaire (XQ) is a brief, 8-item measure of patient-reported xerostomia. Individual items are rated on a 10-point scale with 0 being the minimum and 10 being the maximum on each item. The instrument has demonstrated evidence of internal consistency, test-retest reliability, construct validity, and sensitivity to change [24-26].

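### Removal takes a subject out of the whole study with no provision for later questionnaires, so some xerostomia and QoL outcomes that could still be collected are lost (probably a small effect)

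*Combined protocol and SAP*

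**What the plan says.** Under Investigational Plan, Removal of subject from study, the rule is "Subjects will be removed from the study when any of the criteria listed below apply". Besides withdrawn consent, the list covers failure to meet the protocol's requirements, toxicity (worded as "Subject experiences toxicity that makes continuation in the protocol unsafe"), a treating physician's view that staying in would not serve the patient, and pregnancy.

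After removal, the Principal Investigator is notified, the treating physician makes a note in the medical record, and "The study coordinator will record the reason for removal and date in the Case Report Form". The section does not mention later questionnaires.

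The same part of the protocol describes how packets are collected. Once treatment is over, "the subject will be seen in Radiation Oncology every 3 months for routine follow-up visits related to their radiation treatment", and the packet is completed at those visits. As alternatives to the clinic, it "if necessary can be sent home with the subject with a return envelope, emailed to the subject, or the subject may be called". Study Procedures adds that both planning methods are standard and that the study requires nothing extra during chemo-radiotherapy. The Adverse Events section names loss of confidentiality as the potential risk of taking part.

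Data Handling and Record Keeping asks for data on all registered subjects, but only as the protocol requires. Under Statistical Considerations, xerostomia and QoL are summarised by arm and time point. Mixed models are exploratory. The sample-size paragraph allows for loss by 12 months, using a 17% death-and-dropout figure from a cited trial.

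**The concern.** The plan does not separate leaving the protocol from ending questionnaire follow-up. Toxicity, a physician's judgement and pregnancy do not in themselves prevent a patient-reported form, and some subjects who cannot meet other requirements could still return one. The routes for collecting it already exist. Followed as written, the plan stops asking these subjects.

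The outcomes lost are those the trial exists to describe: xerostomia for the primary objective, and the derived xerostomia rates and QoL for the secondary ones. The protocol itself treats xerostomia as a radiotherapy toxicity, so a toxicity-based removal could plausibly be related to the outcome. If it is, the rates among those who remain describe a selected group. The stated standard errors measure sampling error and do not cover selection. Packets never collected cannot be recovered at analysis, and the estimates are meant to inform larger trials.

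**Working it through.** **The plan's own figures.** Inputs from the sample-size paragraph are 25 per arm and 17% loss.

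- Expected number at 12 months: 25 × 0.83 = 20.75, as stated.
- P(X ≥ 18) for a binomial with n = 25 and probability 0.83 is 0.950, as stated.
- SE of a 50% proportion: √(0.25/25) = 10.0 points and √(0.25/18) = 11.8 points, as stated.

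The sample-size arithmetic is right. The 17% combines death and dropout in another trial, so it gives no count of removals under this protocol's criteria.

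**What one or two lost packets could do.** The following are assumptions:

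- n = 21 observed in one arm at 12 months (20.75 rounded).
- r further subjects removed but alive and willing. With about 25 × 0.17 = 4.25 losses expected from all causes, r = 0, 1 or 2 is a reasonable range.
- p = 50%, the true rate among the n + r.
- q, the share of the r who are cases, is left free.

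The observed rate is [p(n + r) − rq]/n, so the shift is r(p − q)/n. In percentage points:

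| r | all cases (q = 1) | q = 0.75 | q = 0.5 | no cases (q = 0) |
|---|---|---|---|---|
| 0 | 0 | 0 | 0 | 0 |
| 1 | −2.4 | −1.2 | 0 | +2.4 |
| 2 | −4.8 | −2.4 | 0 | +4.8 |

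For example, r = 1 and q = 1 gives (11 − 1)/21 = 47.6%, a shift of −2.4. The outer columns are limits, not expectations.

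**Comparison with sampling error.** √(0.25/21) = 10.9 points, so the limits are 2.4/10.9 = 0.22 SE for one subject and 4.8/10.9 = 0.44 SE for two. With 18 observed, the limits are 0.5/18 = 2.8 and 1.0/18 = 5.6 points, against an SE of 11.8.

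**Dependence on the assumed rate.** For r = 1 and n = 21, using the plan's other two example rates:

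- p = 30%: from −0.7/21 = −3.3 to +0.3/21 = +1.4 points; SE √(0.21/21) = 10.0.
- p = 10%: from −0.9/21 = −4.3 to +0.1/21 = +0.5 points; SE √(0.09/21) = 6.5.

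**Precision.** Recovering the packets adds little here. At 50% the SE goes from 10.9 (n = 21) to √(0.25/22) = 10.7 or √(0.25/23) = 10.4. The gain lies in limiting possible selection.

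**The case against.** The strongest reply is that the recoverable group may be almost empty. Both planning methods are standard, and after treatment participation is mostly forms at routine visits, so it is hard to see toxicity making continuation unsafe. Pregnancy is limited by the urine test and the contraception requirement. The trial is a descriptive pilot with 90% intervals and no planned test or go/no-go rule. This stands, and it is why the point is minor. It does not remove the point: if such subjects are few, so are the extra packets.

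A second reply is that the exploratory mixed models can use packets completed before removal. They can, which is partial mitigation. They do not recover the missing packets, and they are not presented as a method for missing data.

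A third is that the text is merely ambiguous: the data-handling rule covers all registered subjects, the visit schedule makes no exception for removed ones, and the consent form was not available to check. But the data rule reaches only what the protocol requires, and the protocol sets no packet for someone removed from the study. The natural reading is that packets stop.

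A reader might also connect this with the ban on saliva-stimulating drugs and infer that subjects with the worst dry mouth start such a drug, are removed, and so leave the rates too low. The documents do not say that stimulant use triggers removal. That question is separate and needs no extra data field or analysis here.

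**Conclusion.** The point holds as a minor design gap. Removal ends study participation for reasons that need not end questionnaires, and nothing in the protocol or its statistical section provides for the remaining packets. Some collectable outcomes are lost, and bias is possible if removal is related to outcome.

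Its size cannot be estimated from the documents. With 21 observed and a true rate of 50%, the limits are 2.4 points for one such subject in an arm and 4.8 for two, well below the SE of 10.9. With no such subject the effect is zero.

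Three stronger conclusions may be tempting and are not supported. First, the documents do not show that the rates will be biased, or in which direction, for a single arm or for the arm difference. Second, the 17% is not a pool of recoverable outcomes: it is a planning assumption from another trial and includes deaths. Third, 12 months is singled out only for the secondary analyses; the primary objective covers all time points.

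**What to change.** In Removal of subject from study, state that subjects removed for any reason other than withdrawn consent are asked to complete the remaining 3-, 6-, 9- and 12-month packets by the clinic, mail, e-mail or phone routes already allowed, where the subject agrees and the treating physician does not object. State in Statistical Considerations that these data are analysed in the randomised arm. Report the number removed by arm and reason, with deaths shown separately. Leave the clinical removal criteria and the drug rule as they are.

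The cost is an IRB-approved amendment of a sentence or two, a line in the consent form, and a few extra packets to collect. The removal reason and date are already recorded in the CRF, so the added table needs no new field for removals.

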Therefore, we propose to perform a prospective randomized pilot clinical trial, stratified by primary tumor site, to evaluate the degree of xerostomia and quality of life (QOL) in subjects with HN-SQCC treated with radiation therapy under margin-based and robust radiotherapy treatment plans. Margin-based plans will use both biological (biological optimization) and physical objectives whereas robust planning will use physical objectives for sparing of the parotid glands. Intensity-modulated radiation therapy (IMRT) and standard chemotherapy will be used. QOL (quality of life) will be measured using the EORTC QLQ-C30 questionnaire and EORTC QLQ-H&N35 (head and neck) module before radiotherapy (baseline) and then 3, 6, 9 and 12 months after radiotherapy. Xerostomia will be measured in study subjects using two patient-reported scoring systems completed by each subject before radiotherapy and then 3, 6, 9, and 12 months after radiotherapy: the LENT/SOMA grading system and the University of Michigan's Xerostomia Questionnaire (XQ; see Eisbruch *et al.* 2001). The data collected by this randomized pilot clinical trial will be used to inform the design of, and decision-making for, future larger studies that seek to compare different methods of radiotherapy planning in the treatment of HN-SQCC.

STUDY OBJECTIVES

Primary Objective

To evaluate descriptively over time the prevalence and grade of xerostomia in subjects treated for HN-SQCC with IMRT under either biologically optimized margin-based or robust photon radiotherapy.

Secondary Objectives

- 1) To compare descriptively the arm treated with IMRT under the margin-based radiotherapy plan to the arm treated with IMRT under the robust radiotherapy plan for possible differences in derived outcomes of interest, including but not limited to: (1) occurrence rate of grade ≥ 2 xerostomia as determined using the LENT/SOMA scale; and (2) occurrence rate of overall score ≥ 30 on the XQ.
- 2) To obtain NTCP values of the parotid glands from both margin-based and robust radiotherapy treatment plans using validated parameter values of the NTCP mean dose model. Each subject will have their parotid NTCP values computed under both plans, even though they will receive IMRT delivered under only the plan they are randomized to.
- 3) To obtain dose statistics for dose delivered to the parotid glands of each subject via either margin-based or robust treatment plans.

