Quality of Life: The European Organisation for Research and Treatment of Cancer (EORTC) QLQ-C30 [27] is a widely used core module, designed to capture multidimensional aspects of health-related quality-of-life across a wide spectrum of different malignancies. It generates a global score, 5 functional scores, and 9 symptom scores. The H&N35 module [28] assesses concerns specific to head-and-neck cancer patients; it yields 18 symptom scores. Scores on both modules are transformed to a 0-100 scale, with higher scores representing more favorable outcomes on the functioning scales but poorer outcomes on the symptom and head-and-neck-specific scales. In the current study, scales of special interest include dry mouth, oral pain, swallowing, opening mouth, sticky saliva, social eating, and global QOL. Evidence supports the reliability and validity of the EORTC scales [27-29].

Demographic and Clinical Characteristics: Demographic information will be collected at the baseline assessment to record basic background information (e.g., age, race, gender, education, comorbidities, etc.). Clinical variables will be obtained from the treatment team or medical record (e.g., stage, site, recurrence status, prior treatments, time since diagnosis, etc.).

ADVERSE EVENTS

Adverse events associated to study participants

The potential risk to study participants is the potential for loss of confidentiality. Measures to protect the confidentiality of study participants will be implemented as described in the Data Handling and Recordkeeping section.

There will be no direct benefits to the study participants; however, knowledge gained from the study could potentially benefit patients in the future.

Adverse event monitoring

Adverse event data collection and reporting, which is required as part of every clinical trial, is done to ensure the safety of subjects enrolled in the studies as well as those who will enroll in future studies using similar agents. Adverse events are reported in a routine manner at scheduled times during a trial. Additionally, certain adverse events must be reported in an expedited manner to allow for optimal monitoring of subject safety and care.

All subjects experiencing an adverse event will be monitored until the completion of the subject's post-radiotherapy visit:

- the adverse event resolves or the symptoms or signs that constitute the adverse event's return to baseline;

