All other adverse events, such as those that are expected, or are unlikely or definitely not related to the study participation, are to be reported annually as part of regular IRB continuing review.

STATISTICAL CONSIDERATIONS

This is a randomized, two-arm, open-label pilot clinical trial conducted in subjects with squamous-cell carcinoma of the head and neck. Its primary objective is to evaluate descriptively over time the prevalence and grade of xerostomia in subjects treated with IMRT under either biologically optimized margin-based or robust photon radiotherapy of HN-SQCC. Xerostomia will be measured in study subject using two patient-reported scoring systems completed by each subject before radiotherapy and 3, 6, 9, and 12 months after radiotherapy: the LENT/SOMA grading system and the University of Michigan's Xerostomia Questionnaire (XQ; see Eisbruch *et al.* 2001).

To accomplish this study's primary objective, the analysis will proceed as follows: To analyze the XQ, scores on its 8 items will be summed for each subject at each time point to produce an overall XQ score whose values theoretically can range from 0 to 80; it will be treated as a continuous variable. LENT/SOMA grades as written on the form will simply be recorded electronically, and non-integer grades will be allowed if that's what the subject wrote on the form. Longitudinal LENT/SOMA grades will be summarized by treatment arm and time point as the number and proportion of subjects achieving each grade, and also as the mean and SD of grade. Longitudinal overall XQ scores will be summarized by treatment arm and time point as the mean, SD, median, quartiles, and range. Both the correlation between xerostomia measures within each time point and the correlation within each xerostomia measure across time points will be studied using Spearman correlation analysis. Estimated means, SDs, medians, and quartiles will be accompanied by 90% confidence intervals. In exploratory analysis,

we will employ mixed-models analysis to investigate more deeply the interrelationships among the xerostomia measures between treatment arms and time points. Also in exploratory analysis to accomplish the primary objective, we will use means, SD, and ranges to summarize each of the 8 individual items from the XQ by treatment arm and timepoint, and investigate using mixed-models approaches to compare the XQ items descriptively for treatment-arm differences over time.

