- 1) Xerostomia grades from the LENT/SOMA scale will be dichotomized as grade ≥ 2 versus grade < 2 , then summarized by treatment arm and time point as the number and proportion achieving grade ≥ 2 . The dichotomization is placed at grade $</\geq 2$ because that was the cutpoint used in the PARSPORT study [22], but we will also consider an alternative dichotomization at grade $</\geq 3$. As for the overall XQ score (a continuous variable), we will dichotomize it at different cutpoints chosen for their potential clinical relevance, beginning with a cutpoint of $</\geq 30$, then summarize the result by treatment arm and time point as the number and proportion of subjects who surpass the cutpoint. For all dichotomized versions of both xerostomia measures, the proportions on each arm and proportion differences between treatment arms will be estimated at each time point. Estimated proportions and their differences will be accompanied by two-sided 90% confidence intervals. Exploratory mixed-models analysis may be used in follow-up mode, as time permits, to explore more deeply the differences between treatment arms and how they change over time.
- 2) NTCP values from both plans will be summarized by plan and treatment arm as the mean, SD, median, quartiles, and range. Data will be graphed using box plots versus treatment arm. Plans will be compared descriptively by calculating the paired difference between them, and summarizing the result as means, SDs, and ranges. Means will be accompanied by 90% confidence limits.
- 3) Dose statistics on each subject (i.e., the mean, SD, median, 1st and 3rd quartiles, 5th percentile, and 95th percentile of dose received by the subject) will be summarized by statistic and treatment arm as the mean, SD, median, quartiles, and range. Data for each statistics will be graphed using box plots versus treatment arm.
- 4) The global EORTC QOL scale and individual scales for dry mouth, oral pain, swallowing, opening mouth, sticky saliva, and social eating will be summarized by treatment arm and time point as the mean, SD, and range, and also (for individual Likert-scaled items that have 5 or fewer ordered categories) as the

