number and proportion of subjects whose answer falls into each ordered category. Data will be graphed using box plots or scatter plots versus treatment arm and profile plots versus time point. In general, the mean differences between treatment arms will be estimated at each time point, and such estimates will be accompanied by two-sided 90% confidence intervals. Exploratory mixed-models analysis may be used in follow-up mode, as time permits, to explore more deeply the differences between treatment arms and how they change over time.

- 5) Changes in QoL results after treatment (compared to baseline) will be calculated at each post-treatment time point, then assessed for correlation with NTCP values by Spearman correlation analysis.

For analyses in support of the secondary objectives, the outcomes at all time points will be of interest, but outcomes at the 12-month time point will be of special interest because of this time point's prominence in previous studies such as PARSPORT [22].

Sample-size considerations. We plan to consent up to 75 subjects in order to reach our maximum accrual of 50 subjects. Twenty-five subjects will be assigned randomly to IMRT under the margin-based radiotherapy plan, and 25 subjects will be assigned randomly to IMRT under the robust radiotherapy plan.

The IMRT arm of the PARSPORT study [22] lost 17% of its enrolled subjects to death and dropout before they could be evaluated at 12 months for that study's primary endpoint, grade ≥ 2 xerostomia. If similar results hold in our study, and if we enroll 25 subjects per treatment arm, then we can expect the number of subjects who remain on each treatment arm for 12 months to be binomially distributed with expected value of 20.75 and 95% probability of being 18 or higher.

In each analysis, the precision of the estimates can be quantified through their standard errors, with smaller standard errors denoting greater precision. At 3 months, when each treatment arm should still contain 25 subjects, the standard

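### Randomization is stratified by primary tumor site, but the planned 90% intervals for quality-of-life differences between arms do not use site and are wider than needed if site predicts quality of life

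*Combined protocol and SAP*

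**What the plan says.** The design paragraph before STUDY OBJECTIVES describes "a prospective randomized pilot clinical trial, stratified by primary tumor site". The Radiotherapy paragraph under STUDY PROCEDURES repeats that assignment is "determined in a 1:1 randomized fashion with stratification by primary tumor site". Under MEASURES, site is among the variables to be recorded: "Clinical variables will be obtained from the treatment team or medical record (e.g., stage, site, recurrence status".

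In STATISTICAL CONSIDERATIONS, the analysis of secondary objective 4 covers the global QoL scale and six symptom scales, ending with "social eating will be summarized by treatment arm and time point as the mean, SD, and range". As its usual approach to comparing the arms, it then states: "the mean differences between treatment arms will be estimated at each time point, and such estimates will be accompanied by two-sided 90% confidence intervals". It adds: "Exploratory mixed-models analysis may be used in follow-up mode, as time permits". For the secondary objectives, "outcomes at the 12-month time point will be of special interest".

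For the primary objective the same section says, as exploratory work, "we will employ mixed-models analysis to investigate more deeply the interrelationships among the xerostomia measures between treatment arms and time points". Neither set of mixed models has its terms listed. STATISTICAL CONSIDERATIONS does not mention site or stratification, and no part of the document defines the site categories.

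**The concern.** Stratifying on site makes the arms similar in site mix. If site predicts QoL, this removes most of the between-site variation from the arm difference. An unadjusted two-sample interval still counts that variation as noise. It is then wider than its nominal level requires and covers more often than 90%.

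What is at stake is reported precision only. The trial exists to supply estimates for planning larger studies and justifies its sample size by precision, so interval width is a reasonable thing to look at. It is most relevant at 12 months, where the plan allows for as few as 18 subjects per arm. These are descriptive analyses of a secondary objective, with no hypothesis test.

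**Working it through.** **Inputs from the plan.** 25 subjects per arm; 17% loss by 12 months; as few as 18 per arm at 12 months; two-sided 90% intervals; QoL scales from 0 to 100.

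**Assumptions (not in the documents).** Number and mix of sites, block size 4, equally spaced site means, R2 (share of QoL variance explained by site), and a QoL SD of 20 to 30 points.

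**1. The plan's own figures.** The standard error of an arm mean is SD/√n: 1/√25 = 0.200 and 1/√18 = 0.236. Expected retention is 25 × 0.83 = 20.75, and the binomial probability of 18 or more is 0.9505. All agree with the plan. They describe single arms, not differences.

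**2. Unadjusted half-width for a difference**, in SD units: t(0.95; 2n-2) × √(2/n).
- n = 25: 1.677 × 0.2828 = 0.474
- n = 18: 1.691 × 0.3333 = 0.564

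**3. Site-adjusted half-width under perfect balance**, k sites: t(0.95; 2n-2-(k-1)) × √(1-R2) × √(2/n). With k = 4:

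| R2 | 0 | 0.05 | 0.10 | 0.20 | 0.30 |
|---|---|---|---|---|---|
| n = 25 | 0.475 | 0.463 | 0.451 | 0.425 | 0.397 |
| n = 18 | 0.565 | 0.551 | 0.536 | 0.506 | 0.473 |

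**4. Simulation with incomplete blocks and loss.** 50 subjects, 17% random loss, linear model with arm and site, 8000 trials per setting. A site with fewer than 4 randomized subjects joins the next smallest. Site mixes: 50/30/20%, 40/30/20/10% and 35/25/20/10/10%. Monte Carlo error of coverage is about 0.3 points.

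| R2 | Change in mean width: 3 / 4 / 5 sites | Unadjusted coverage |
|---|---|---|
| 0 | +0.6 / +1.1 / +1.4% | not tabulated |
| 0.02 | -0.3 / +0.1 / +0.4% | not tabulated |
| 0.05 | -1.9 / -1.5 / -1.1% | 90.4-90.8% |
| 0.10 | -4.4 / -4.2 / -3.8% | 90.7-91.3% |
| 0.20 | -10.1 / -9.6 / -9.2% | 92.2-92.5% |
| 0.30 | -16.1 / -15.4 / -15.0% | 93.7-94.2% |

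Adjusted coverage was 89.2-90.6% throughout. Break-even is at R2 of about 0.02 to 0.03. With exactly 18 per arm (4 sites, two smallest merged) the changes are +1.2, -1.3, -3.8, -8.9 and -14.4% at R2 0, 0.05, 0.10, 0.20 and 0.30.

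**5. What these R2 values require.** The gap between extreme sites is √(R2/v) in SD units, where v is the variance of the site positions scaled to 0-1. For 4 sites v = 0.111, so R2 = 0.10 gives √(0.10/0.111) = 0.95 SD.

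| R2 | Gap (SD) | Gap in points, SD 20-30 |
|---|---|---|
| 0.05 | 0.67 | 13-20 |
| 0.10 | 0.95 | 19-28 |
| 0.20 | 1.34 | 27-40 |
| 0.30 | 1.64 | 33-49 |

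**6. Gain in points (4 sites, 17% loss).** At R2 = 0.10 the half-width falls from 0.523 to 0.501 SD: 0.022 × 20 to 0.022 × 30 = 0.4 to 0.7 points. At R2 = 0.20 it falls from 0.523 to 0.473 SD: 1.0 to 1.5 points.

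**7. The estimate itself.** With 4 sites its SD is 0.302 unadjusted and 0.300 adjusted at R2 = 0.10, 0.291 and 0.284 at 0.20, and 0.274 and 0.262 at 0.30. Its mean stays within 0.006 SD of the true zero with or without adjustment.

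**8. Merging (4 sites, R2 = 0.20).** Without merging the width changes by -9.7%. Always merging the two smallest sites gives -9.4% if their means are adjacent, but only -2.0% if they are the two extremes. The fewer-than-4 rule gives -9.6% and -8.8% in the same two cases. A site had subjects in one arm only in about 11% of trials without merging and about 2% with that rule.

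**The case against.** The strongest reply is that this is a modelling preference in a descriptive pilot. Several parts of it stand.

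- The precision figures under Sample-size considerations are single-arm standard errors. Site adjustment of a difference changes none of them.
- The estimator hardly becomes more precise: stratified allocation has already delivered that gain. What changes is mainly the reported width, and the unadjusted interval errs on the safe side.
- The mean width hides variation from trial to trial. In 4000 simulated 4-site trials per setting, the adjusted interval was the wider one in 70% of trials at R2 = 0, 60% at 0.02, 44% at 0.05 and 26% at 0.10.
- The documents give no link between site and QoL and no interval formula. Because the mixed models have no listed terms, adding site would not contradict the plan.
- A second set of intervals at all five time points includes baseline, before any treatment effect can exist.

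These arguments limit the importance of the point. They do not remove it: the design uses site, the plan commits to between-arm intervals, and nothing in the plan calls for site in computing them.

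**Conclusion.** The point holds in its conditional form and is optional. The planned QoL intervals name no site term, although site is the stratification factor and is collected. If site explains about 10% of QoL variance, the unadjusted intervals are conservative and adjustment makes them about 4% narrower on average; at 20% the gain is about 10%. At 5% it is under 2%, and if site is irrelevant, adjustment widens the intervals by about 1%.

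These sizes rest on the assumed R2, site mix, equally spaced site means and block size. The larger gains need site differences that the documents neither support nor exclude. There is no bias and no wrong figure.

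**What to change.** For secondary objective 4, report beside each unadjusted QoL mean difference a site-adjusted one with a two-sided 90% interval, from a linear or mixed model with arm and site as factors. Limiting this to 12 months is reasonable. Include site as a factor in the exploratory mixed models for the Xerostomia Questionnaire (XQ).

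List the site categories and fix a merging rule before analysis: for example, a site with fewer than 4 randomized subjects joins the next smallest. Do not merge sites that are not sparse, because that can lose most of the gain.

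The cost is SAP wording and extra reporting: 7 scales × 5 time points = 35 intervals, or 7 at 12 months only. No new data are needed. If site is unrelated to QoL, the adjusted intervals are on average 0.6 to 1.4% wider; the unadjusted results remain in the report.
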